**Study Procedures:** 1. PA/A studies: PA/A will be primarily measured by ex-vivo aggregometry (3 ml). In addition, secondary exploratory measures of PA/A will be assessed through flow cytometric detection of p-selectin and activated surface glycoprotein (GP) IIb/IIIa receptor. For platelet aggregometry and flow cytometry, studies will be promptly performed after specimen collection. Samples will be gently centrifuged to separate platelet-rich plasma (PRP) from white and red blood cells and platelet-poor plasma (PPP). PA/A will be assessed by a Multiple Analyzer (MA) after addition of an adenosine diphosphate (ADP) agonist to PRP. Although patients will be on aspirin, primary assessment of PA/A by aggregometry with ADP [ $>1\mu\text{m}$ ] in aspirin exposed platelets is preserved [26]. Aggregation is plotted against time. The maximum height of the curve represents the aggregation level, the slope is the reaction velocity, and the area under the curve (AUC) is calculated as the main aggregation measure, given in arbitrary units (AU) [12]. This ADP induced AUC will be the primary measure of PA/A in this proposal. P-selectin is a cell-adhesion glycoprotein which is present in the alpha granules of platelets. When platelets are activated, p-selectin localizes to the surface to mediate adhesion to other activated platelets, endothelial cells and leukocytes. Platelet membrane GPIIb/IIIa is a member of the integrin family of cell-membrane receptors that plays a key role in platelet aggregation and thrombus formation. Expression of activated GPIIb/IIIa receptors is exquisitely related to the PA/A. Both p-selectin and activated GP IIb/IIIa receptor in PRP will be measured through flow cytometry as previously described [17]. Prior to sample collection, 3 ml of blood will be wasted to eliminate the impact of venipuncture on PA/A. As the contemplated studies progress, the Platelet Activity State (PAS) Assay, which has been defined by our collaborating group by [name], will be added as an exploratory measure. The PAS assay evaluates mechanical shear-mediated platelet activation [27, 28].

2. Platelet cGMP: Whole-blood samples (3 ml) anticoagulated with citrate will be centrifuged to obtain PRP. Platelet cGMP will be quantified as described previously [35] by cGMP ELISA Kit (Cayman Chem., USA).

3. VWF studies: Standard gel electrophoresis will be conducted on plasma samples (3 ml). A

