**Statistical analysis, sample size calculations and timeline:** The primary measure for PA/A is ADP-induced AUC assessed by platelet aggregometry. ADP-induced AUC will be compared between the LLH and no LLH groups with an unpaired Student's t test. The null hypothesis is that there will be no difference in the PA/A between groups. A prior in-vitro study suggested that LLH increases PA/A by at least 30% as measured by aggregometry from  $20\pm 5$  to  $26\pm 4$  AU [12]. If this is the true population effect of LLH on PA/A in patients with CF pumps, with a minimum of 15 patients in each group per device we would achieve **90% power** to detect a significant difference in means with a two-sided alpha of 0.05. Since there will be fewer patients with LLH, we will recruit for both groups until we have enrolled 15 patients in the LLH group for each device. As device specific comparisons will be made, for durable CF pumps we estimate that we will have to screen 80 HM2 and 115 HM3 patients. We estimate that 35% of these patients will be excluded due to being on sildenafil, nitrates, active infection or withholding consent. This will leave 50 HM2 and 75 HM3 patients available for analysis. From historical data [30], we expect that approximately 30% of HM2 (n=15) patients and 20% of HM3 (n=15) will have LLH and the remainder will be in the no LLH group (35 HM2, 60 HM3). For acute CF pump support, we estimate that 90 VA ECMO and 90 Impella patients will need to be screened and after 50% exclusion, 45 VA ECMO and 45 Impella will be enrolled and available for analysis. Based on our preliminary data (**Figure 3C**) for VA ECMO and prior reports in Impella [31], we expect that at least 35% of patients for each acute CF pump (n=15 per device) will have LLH and the remainder will be in the no LLH group (n=30). At our institution there are 5 durable CF pumps implants (3 HM3 and HM2) and 6 acute support CF pumps (3 VA ECMO and 3 Impella) implanted every month. In addition, there are currently 125 stable outpatients with durable CF pumps (95 HM2 and 30 HM3) available for screening. Therefore, we estimate it would take 32 months to enroll and analyze the calculated number of patients for all devices (see timeline). For each device specific comparison, we will examine the confounding effects of age, sex, body mass index, race/ethnicity (such variables are known to effect

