**Statistical analysis, sample size calculations:** The primary measure of PA/A is the change in ADP-induced AUC assessed by platelet aggregometry, which will be compared between the treatment and placebo groups by an independent samples Student's t test. The null hypothesis is that the mean change in PA/A will be the same in both groups at the 15 day time-point. In a prior single-arm study in patients with ongoing hemolysis from SCA, sildenafil reduced PA/A by around 40% from  $30.6\%\pm15.2$  to  $17.3\%\pm12.4$  [17]. If this is the true population effect with standard deviation of the sildenafil induced change in PA/A among patients on durable CF pump support and if there is no expected change in the placebo group, we would need 23 patients per group (46 total patients) to achieve **85% power** to detect a significant difference in mean reduction with a two-sided alpha of 0.05. Analysis will be by intention-to-treat. Although the primary analysis will be unadjusted, secondary analyses will apply linear regression models to adjust for age, sex, race/ethnicity, duration of device implant, type of device (HM2 or 3) and adherence. Given the small sample, adjustment will be limited to no more than 2 additional variables at a time. If device differences are observed, sub-group analyses by device will be performed. For secondary outcomes, the above analyses will be repeated at 8 days and also comparisons of changes in p-selectin, activated GP IIb/IIIa receptor and platelet cGMP at 8 and 15 days.

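### Aim 2's 85% power at 23 per group is not supported for its primary endpoint: the planning effect is in percent, the endpoint is in arbitrary units, and no SD of change is given

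*Combined protocol and SAP*

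**What the plan says.** The statistical paragraph of Aim 2 defines the endpoint: "The primary measure of PA/A is the change in ADP-induced AUC assessed by platelet aggregometry". The groups are "compared between the treatment and placebo groups by an independent samples Student's t test", and the null hypothesis is that "the mean change in PA/A will be the same in both groups at the 15 day time-point". The unit is set in the Aim 1 Study Procedures, where "the area under the curve (AUC) is calculated as the main aggregation measure, given in arbitrary units (AU) [12".

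The planning effect comes from reference 17: "In a prior single-arm study in patients with ongoing hemolysis from SCA, sildenafil reduced PA/A by around 40% from" 30.6%±15.2 to 17.3%±12.4. The power statement follows on the condition "If this is the true population effect with standard deviation of the sildenafil induced change in PA/A among patients on durable CF pump support". It assumes no change on placebo and arrives at 23 per group (46 in total), 85% power and two-sided alpha 0.05.

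Reference 17 is also cited in the Aim 1 Study Procedures, as a method: "Both p-selectin and activated GP IIb/IIIa receptor in PRP will be measured through flow cytometry as previously described [17". Those markers are secondary exploratory measures there.

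The addendum under Aim 2 says that 46 is no longer feasible. It adds an interim analysis at 20 completers and allows the sample size to be readjusted if a trend at p<0.2 is seen. It names no target effect and no SD for that step.

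**The concern.** A power figure for a t test on changes needs a mean difference in change and an SD of change, both on the endpoint's scale. Here the difference is in percent from another population, while the endpoint is in AU. The two printed SDs describe levels before and after treatment. The paragraph refers to an SD of change in words but gives no number, so a reader cannot tell which SD produced 23 per group.

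Two things depend on this. The 85% is the only statement of what Aim 2 was designed to detect, and it does not translate into a detectable difference in AU. The addendum also opens the sample size to revision without naming inputs. Unless something else is specified, the percent-scale figures are the only planning values for Aim 2 in the document.

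**Working it through.** **Inputs.** From the Aim 2 statistical paragraph: means 30.6 and 17.3, SDs 15.2 and 12.4 (percent scale), placebo change 0, n = 23 per group, two-sided alpha 0.05, stated power 85%. The pre-post correlation r is not given and is assumed below.

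**Difference.** 30.6 − 17.3 = 13.3 percentage points, a relative fall of 13.3/30.6 = 43.5%.

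**Can the plan's figure be reproduced?** Take the baseline SD of 15.2 as if it were the SD of change.
- Normal approximation: n = 2 × (1.960 + 1.036)² × 15.2² / 13.3² = 23.4 per group.
- Power at 23 per group is 84.3% by the normal approximation and 82.7% by the noncentral t.

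So 23 and 85% come out approximately, but only by using an SD of a level where an SD of change is needed. Another route lands nearby: a rounded 40% effect (0.40 × 30.6 = 12.24) with the average of the two variances, SD = √((15.2² + 12.4²)/2) = 13.87, gives about 24 per group and 83.3% power at 23. Since more than one route leads close to 23, the SD actually used cannot be traced.

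**SD of change implied by the printed SDs.** SD = √(15.2² + 12.4² − 2r × 15.2 × 12.4). Power is by the noncentral t at 23 per group.

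| Assumed r | SD of change | 13.3 / SD | Power |
|---|---|---|---|
| 0 | 19.6 | 0.68 | 61% |
| 0.3 | 16.5 | 0.81 | 76% |
| 0.5 | 14.0 | 0.95 | 88% |
| 0.6 | 12.6 | 1.06 | 94% |

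**What 85% requires.** With 23 per group, 85% power corresponds to a difference of 0.903 SDs of change. The SD must then be 13.3/0.903 = 14.7, so r = (15.2² + 12.4² − 14.7²)/(2 × 15.2 × 12.4) ≈ 0.45. Neither value is in the documents.

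**AU scale.** The documents give no effect of sildenafil on AUC and no SD of its change. As an illustration only, carry a 40% relative fall over to Aim 1's AU figures (20±5 and 26±4), with equal pre and post SDs and r = 0.
- From 20 AU: fall 8.0, SD = √2 × 5 = 7.07, power 96%.
- From 26 AU: fall 10.4, SD = √2 × 4 = 5.66, power over 99%.

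**The case against.** The best defence is that no arithmetic error is shown, and that stands. The stated figure roughly reproduces with 15.2 as the SD of change, and 85% lies inside the range that the printed SDs produce. The paragraph is also openly conditional on the effect carrying over, and t-test power depends only on the standardized effect, so a change of unit does not by itself invalidate it. What is missing is the standardized effect itself: without an SD of change there is none, and no reason is given why a percent-scale effect in sickle cell anemia should equal the standardized effect on AUC in pump patients.

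Four stronger readings are tempting, and the documents do not support them.
- *The 30.6% and 17.3% are flow cytometry results.* The assay behind them is not named. Reference 17 is cited for flow cytometry elsewhere, which makes this plausible but does not establish it. The percent-versus-AU mismatch does not depend on it.
- *The effect contradicts Aim 1's AU figures.* Those are introduced with "A prior in-vitro study suggested that LLH increases PA/A by at least 30% as measured by aggregometry". The plan makes them neither Aim 2's baseline nor a ceiling on the drug effect, and Aim 2 defines low-level hemolysis differently.
- *A null result could not be interpreted.* It can, from the confidence interval for the difference in AUC change.
- *The addendum will readjust from the percent-scale figures.* It does not say so; it names no inputs.

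It is also fair to say that the target of 46 has been overtaken. That lowers the value of repairing the old statement but raises the value of specifying the inputs to any new one.

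**Conclusion.** The 85% power at 23 per group is not supported for change in ADP-induced AUC. Two gaps are plain on the page: the planning effect is on a different scale from the endpoint, and the SD of change is never given. On the percent scale, power at 23 per group runs from 61% to 94% over assumed pre-post correlations of 0 to 0.6, and 85% holds only near an SD of change of 14.7. The range rests on the printed SDs applying to Aim 2 and on the correlations, which are assumptions.

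A reader might infer that Aim 2 is underpowered. That does not follow: if a 40% fall carried over to AU with Aim 1's SDs, power would be 96% to over 99%. The conclusion is that the figure cannot be relied on in either direction. This should be corrected, chiefly because the sample size may still be revised.

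**What to change.** 1. Replace the 85% statement with the detectable difference in AUC change, in AU, at the sample size now achievable. Show the assumed SD of change and pre-post correlation, with a range. At 23 per group the detectable difference for 85% power is 0.903 times the SD of change; at a smaller size the multiple is larger.
2. For the addendum, state in advance a target change in AUC, in AU. Base any readjustment on that target and the SD of AUC change in the 20 completers, not on the percent-scale figures.
3. Say whether that SD is blinded (all 20 together) or pooled within arm. Note its imprecision: with 18 degrees of freedom the 95% interval runs from about 0.76 to 1.48 times the estimate, so the resulting size should be shown over that range.

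The cost is a rewritten paragraph and a calculation on data already collected, with no extra patients for the correction itself. The downside is that the stated power may become less favourable.

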**Study Protocol:** After obtaining informed consent, baseline demographics and hematologic biomarkers including fasting am PA/A and NO bioavailability measurements (3 tubes [1 tube for platelet aggregometry, 1 tube for exploratory biomarkers including p selectin, CD 40L, GPIIb/IIIa receptor, and 1 tube for NO bioavailability] x 3ml = 9 ml of blood) will be collected. In addition, endothelial function will be assessed by flow mediated dilation of the brachial artery and fingertip temperature changes following a 5 min blood pressure cuff inflation. Patients will be placed, using computerized randomization, into 2 groups to receive the study drug which will be either sildenafil or placebo. More precisely, an enrolled patient will be randomly placed in either the placebo or the sildenafil arm, both of which will be marked as "Study Drug." Neither the patient nor the drug administrator will be aware to which study arm the patient has been designated. Following randomization and if BP is in the acceptable range (see figure 4), 20 mg of the study drug will be administered. Then BP will be recorded every 30 mins for two hours. If BP drop is < 5 mmHg after 2 hours and patient is asymptomatic, they will proceed to take 20 mg of the study drug every 8, starting on day 2 (total 18 doses). Patients will be asked to return to the clinic on day 8 and 20 mg of the study drug will be administered. After 2 hours, which is the time of peak drug concentration, fasting am PA/A and NO bioavailability measurements (3 tubes [1 tube for platelet aggregometry, 1 tube for exploratory biomarkers including p selectin, CD 40L, GPIIb/IIIa receptor, and 1 tube for NO bioavailability] x 3ml = 9 ml of blood) will be collected. In addition, endothelial function will be assessed by flow mediated dilation of the brachial artery and fingertip temperature changes following a 5 min blood pressure cuff inflation. Then the patient will be asked to come back to clinic on the next weekday and if BP is in the acceptable range (see figure 4), 40 mg of the study drug will be administered. If BP remains stable for 2 hours (< 5 mmHg drop and asymptomatic), then patients will continue taking 40 mg every 8 hours. Patients will be asked to return to clinic on day 15. A final 40 mg dose of the study drug will be given and after 2 hours fasting am PA/A and NO bioavailability measurements (3 tubes [1 tube for platelet aggregometry, 1 tube for exploratory biomarkers including p selectin, CD 40L, GPIIb/IIIa receptor, and 1 tube for NO bioavailability] x 3ml = 9 ml of blood) will be collected. In addition, endothelial function will be assessed by flow mediated dilation of the brachial artery and fingertip temperature changes following a 5 min blood pressure cuff inflation. All patients will be on a standard antithrombotic regimen of aspirin 81 mg daily with a target INR of 2-2.5 IU.

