
Endothelial Function Testing will be conducted by non-invasive methodology. As has been previously well described [32], a vascular ultrasound probe will be used to assess the diameter of the brachial artery at the level of the antecubital fossa in the longitudinal view. Then an arm blood pressure cuff will be inflated beyond the systolic pressure for 5 minutes to cause transient ischemia. After deflation of the arm blood pressure cuff, the brachial artery diameter will be recorded again by the ultrasound vascular probe. In addition, by using the noninvasive Endothelix device, we will simultaneously also record figure tip temperature change before and after cuff deflation, as another measure of endothelial function.

Addendum to study protocol:

Aim 2 of this protocol is a randomized, blinded, placebo-controlled study to assess the effect of sildenafil on platelet function in patients supported by left ventricular assist devices. We originally proposed to enroll 46 patients into this study. At this point, 20 participants have successfully completed the study since enrollment which was initiated in 2019. Due to slower than expected enrollment for a variety of reasons, including the COVID-19 pandemic, a competing trial and a reduction in institutional implantation volume of these devices, it is no longer feasible to reach the originally proposed sample size within the planned study period

ending December 30, 2023.

In discussion with my mentoring team, we propose to amend the study protocol to perform an interim analysis at the current sample size of 20 participants. The statistical plan will be carried out as originally proposed in the study plan. If there is a trend at a  $p<0.2$  for a change in platelet function between groups, then we will readjust the required sample size accordingly for the duration of the enrollment period. If this trend is not apparent, then it would be futile to enroll additional patients into this study aim and further enrollment will stop. In this scenario, we will proceed with analysis of proposed study measures with subsequent reporting of findings.

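### Aim 2's primary t test on change leaves baseline ADP-induced AUC out as a covariate; ANCOVA on data already collected would be more precise at low to moderate baseline/day-15 correlation

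*Combined protocol and SAP*

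**What the plan says.** Under Aim 2, Statistical analysis, sample size calculations, the endpoint is defined as follows: "The primary measure of PA/A is the change in ADP-induced AUC assessed by platelet aggregometry". The arms are compared by an independent-samples t test at day 15, by intention to treat. On covariates the plan states: "Although the primary analysis will be unadjusted, secondary analyses will apply linear regression models to adjust for age, sex, race/ethnicity, duration of device implant". The list ends with "type of device (HM2 or 3) and adherence", and "adjustment will be limited to no more than 2 additional variables at a time". Baseline AUC is not on it.

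Aim 2, Study Protocol has the following collected after consent: "baseline demographics and hematologic biomarkers including fasting am PA/A and NO bioavailability measurements". One of the tubes is for aggregometry. Randomisation comes next in the sequence described.

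The Addendum to study protocol adds an interim analysis of the 20 completers. It states: "The statistical plan will be carried out as originally proposed in the study plan". Without a trend at p<0.2, enrolment stops; with one, the sample size is readjusted. The addendum names neither the test nor the day for this look.

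**The concern.** A pre-randomisation measurement of the outcome is usually the strongest covariate available. Here it enters only by subtraction. A change score fixes the baseline slope at 1, whereas ANCOVA estimates the slope from the data. When the true slope is well below 1, subtraction adds noise.

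Two things are at stake. The first is power at the planned 23 per arm, which does not depend on how the interim look is read. The second is the interim decision. The natural reading of the addendum is that the same t test is used there, so the lost precision bears on whether enrolment continues. The addendum also says the planned 46 can no longer be reached, so the loss cannot be made good by recruiting more patients.

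A separate, minor point concerns adherence, which arises after randomisation. Secondary models that include it do not estimate the intention-to-treat effect. The primary analysis is unaffected.

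**Working it through.** **Inputs from the plan.** The Aim 2 sample-size paragraph takes 30.6% (SD 15.2) before and 17.3% (SD 12.4) after sildenafil from a single-arm sickle cell study. The difference is 30.6 − 17.3 = 13.3. It assumes no change on placebo, two-sided alpha 0.05 and 23 per group for 85% power. It prints no SD of change.

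**Assumptions.** r is not given, so a range is shown. The 20 completers are taken as 10 per arm. The prior data are percentages, while Aim 1, Study Procedures gives AUC in arbitrary units. The figures therefore assume that the standardised effect 13.3/15.2 = 0.875 baseline SD carries over.

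**Reproducing the plan's figure.** With 15.2 as the SD of change, the normal approximation gives 24 per group and 84.3% power at 23. The noncentral t gives 25 per group and 82.7%. The stated 23 is thus reproduced within rounding.

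Exactly 85% at 23 per group needs 13.3/SD = 0.9035, so SD of change = 14.72. With SDs 15.2 and 12.4 this implies

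r = (15.2² + 12.4² − 14.72²)/(2 × 15.2 × 12.4) = 168.1/377.0 = 0.446.

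With equal SDs of 15.2 it implies r = 1 − 14.72²/(2 × 15.2²) = 0.53. If the planners simply used 15.2 as the SD of change, the 23 says nothing about r.

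**Formulae.**
- Change score: variance = s0² + s1² − 2r·s0·s1. With equal SDs, SD = 15.2·√(2(1 − r)).
- ANCOVA: residual variance = s1²(1 − r²), times 1 + 1/(2n − 4) for chance baseline imbalance, with one degree of freedom fewer.
- Ratio with equal SDs: (1 + r)/2 before that small-sample factor. At r = 0.45 and 10 per arm: 0.725 × 1.0625 = 0.77.

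**Results, equal SDs of 15.2, difference 13.3** (t test by noncentral t; ANCOVA by simulation under bivariate normality):

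| r | SD of change | Power, 23 per arm: t test | ANCOVA | Chance of p≥0.2, 10 per arm: t test | ANCOVA |
|---|---|---|---|---|---|
| 0.2 | 19.2 | 63% | 83% | 41% | 27% |
| 0.3 | 18.0 | 69% | 85% | 37% | 25% |
| 0.45 | 15.9 | 79% | 89.5% | 29% | 21% |
| 0.53 | 14.7 | 85% | 92% | 24% | 18% |
| 0.6 | 13.6 | 90% | 95% | 20% | 15% |
| 0.8 | 9.6 | >99% | >99% | 4% | 4% |
| 0.9 | 6.8 | >99% | >99% | <1% | <1% |

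**Unequal SDs, r = 0.446.** The plan gives 12.4 only as the SD after sildenafil, so both readings are shown.

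| Follow-up SD of 12.4 in | Power, 23 per arm: t test | ANCOVA | Chance of p≥0.2, 10 per arm: t test | ANCOVA |
|---|---|---|---|---|
| Sildenafil arm only (placebo 15.2) | 82% | 94% | 27% | 16% |
| Both arms | 85% | 98% | 24% | 10% |

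**Checks.** An 8/12 split at r = 0.45 gives a chance of p≥0.2 of about 31% against 22 to 23%. Type I error at 10 per arm is 0.05 for both methods.

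**The case against.** The strongest reply is that nothing here is an error. The plan prespecifies endpoint, test, day and analysis population, and its sample size matches its test. ANCOVA is a sharper choice among valid ones. That stands, and it limits how heavily the point should weigh.

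The low-r rows also sit badly with the plan's own 85%: at r = 0.2 or 0.3 with equal SDs, the t test has only 63% or 69% power at 23 per arm. If the 85% is taken at face value, r is about 0.45 to 0.53. With equal SDs and r = 0.53, the gain is about 7 points of power and 6 points of stopping risk. That is fair, and it is the better anchor. But the SD of change is not printed, so lower values of r cannot be excluded, and nor can values of 0.8 or more, where nothing is gained.

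The risk of stopping wrongly at 20 completers comes mainly from the p<0.2 rule at that size. ANCOVA reduces it but leaves 18% at r = 0.53. This is also correct.

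Finally, replacing a prespecified primary test late needs justification, and the documents do not show whether unblinded data had been seen when the addendum was written. That restricts which remedy is open but does not remove the point.

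**Conclusion.** The concern holds as a loss of efficiency, not of validity. Baseline AUC is available, precedes randomisation and is not used as a covariate. Where the plan's 85% power is taken as exact, ANCOVA raises power at 23 per arm from 85% to 92% (equal SDs, r = 0.53), from 82% to 94% (12.4 in the sildenafil arm only, r = 0.446) or from 85% to 98% (12.4 in both arms). The gain is larger at lower r and almost nil at r of 0.8 or more with equal SDs. All figures rest on an unknown r and on a sickle cell effect in percent carrying over to AUC. The interim figures also assume the 10/10 split and that the look uses the primary test. The change should be made if the blind is intact. Confidence in the size of the gain is moderate.

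**What to change.** If no unblinded data have been examined:

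- Make the primary analysis an ANCOVA of day-15 ADP-induced AUC on arm, with baseline AUC as covariate. State that baseline does not count towards the two-variable limit.
- Name this model and day 15 as the test for the p<0.2 look, and use it for the sample-size readjustment.
- Use the same form at day 8 and for other markers that have a baseline value.
- Keep the t test on change as a sensitivity analysis.

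If unblinded data have been seen, keep the t test as primary and add the ANCOVA as a labelled sensitivity analysis.

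Separately, remove adherence from the covariate list and report it by arm, or label the models that include it exploratory.

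The cost is one degree of freedom and no new data. At 10 per arm and r = 0.9 with equal SDs, the loss of power at the 0.05 level is about 0.2 percentage points (98.5% against 98.3%). The primary-analysis paragraph and the addendum's interim rule must be reworded.

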### **Data Safety Monitoring Plan:**

A data safety monitoring board (DSMB) will be created to review adherence to study protocol and breaks in confidentiality. In addition, any side effects or complications associated with phlebotomy such as bruising or with the initiation of sildenafil therapy including headache, dizziness and hypotension will be carefully tracked. Since sildenafil is typically well tolerated in patients with CF pumps the potential risks are likely minimal. The DSMB will be external and will consist of a heart failure attending cardiologist. [REDACTED]

Adverse event monitoring will be continuously done throughout the study period and a log of any AE's will be kept in an excel file. The DSMB will produce quarterly reports of adverse events that may have occurred during phlebotomy or after administration of drug therapy. To ensure accuracy of data, all adverse events will be verified [REDACTED]. If

greater than or equal to 2 patients experience any significant side effects of phlebotomy or sildenafil therapy, then the protocol will be halted until further notice by the DSMB. These adverse events will be communicated to the IRB by the PI ([name]).

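### Aim 2's secondary regressions adjust for adherence, which arises after randomisation, so any model that includes it is not a randomised comparison

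*Combined protocol and SAP*

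**What the plan says.** All references are to the combined protocol and SAP.

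- **Aim 2, Statistical analysis, sample size calculations.** The primary comparison is a t test on change in ADP-induced AUC at day 15. The plan states "Analysis will be by intention-to-treat" and continues "Although the primary analysis will be unadjusted", after which "secondary analyses will apply linear regression models to adjust for age, sex, race/ethnicity, duration of device implant, type of device (HM2 or 3) and adherence". Because the sample is small, "adjustment will be limited to no more than 2 additional variables at a time". For secondary outcomes the same analyses are to be repeated at day 8.
- **Aim 2, Study Protocol.** Dosing starts after allocation: "Following randomization and if BP is in the acceptable range", a first 20 mg dose is given. For repeated 20 mg dosing the rule is "If BP drop is < 5 mmHg after 2 hours and patient is asymptomatic, they will proceed to take" the study drug every 8 hours. The first 40 mg dose again depends on BP being in an acceptable range, for which the text refers to Figure 4. For continuing at that level, "If BP remains stable for 2 hours (< 5 mmHg drop and asymptomatic), then patients will continue taking 40 mg every 8 hours".
- **Data Safety Monitoring Plan.** Side effects associated with "initiation of sildenafil therapy including headache, dizziness and hypotension will be carefully tracked".

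The plan does not define adherence, say how it is measured, or say whether a dose withheld under the BP rule counts against it. It gives the adherence-adjusted model no separate label or target effect.

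**The concern.** Age, sex, race/ethnicity, implant duration and device type are settled before allocation. Randomisation balances them in expectation, so adjusting for them leaves the treatment comparison a randomised one. Adherence is settled afterwards and may itself be a consequence of the arm. Comparing sildenafil and placebo patients at the same adherence level may then compare different kinds of patient. For example, those who keep taking an active drug despite its effects on BP need not resemble those who keep taking placebo. The plan lists all six variables together under an intention-to-treat heading, so a reader of the results would have no signal that one of these models means something different from the others.

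What is at stake is the interpretation of those secondary models at days 15 and 8. The main result of the trial is not at stake.

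**Working it through.** **1. Which covariates precede randomisation?** Five of the six do. Adherence does not.

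**2. Could adherence depend on arm?** Both tests of a BP drop under 5 mmHg without symptoms follow randomisation and follow a dose of study drug. The safety section names headache, dizziness and hypotension as effects to track on sildenafil. A difference by arm is therefore plausible, but the documents give no rate for it.

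**3. The plan's own sample size.** The design effect is 30.6 − 17.3 = 13.3 points, with no change expected on placebo. The SD of the change is not stated. With SD 15.2 (the pre-treatment SD in the cited sickle cell study), the normal formula gives 24 per group and the t version 25; power at 23 per group is 84.3% or 82.7%. Conversely, 85% power at 23 per group implies an SD of 14.7 (t) to 15.1 (normal). The stated 23 is thus reproduced closely, and 14.7 is used below. This calculation concerns the unadjusted test only.

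**4. Shift caused by adjusting.** In a linear model with a common adherence slope:

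adjusted effect = unadjusted effect − slope × (mean adherence on sildenafil − mean adherence on placebo).

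With adherence in within-arm SD units, the slope is r × 14.7, where r is the within-arm correlation of adherence with PA/A change. If adherence is D SDs lower on sildenafil, the shift is D × r × 14.7. Both D and r are assumptions; the documents give neither.

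- D = 0 or r = 0: shift 0
- D = 0.5, r = ±0.35: 0.5 × 0.35 × 14.7 = 2.6
- D = 1, r = ±0.35: 1 × 0.35 × 14.7 = 5.1

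Adjusted effect when the unadjusted effect is −13.3:

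| D (SD lower on sildenafil) | r = 0 | r = +0.35 | r = −0.35 |
|---|---|---|---|
| 0 | −13.3 | −13.3 | −13.3 |
| 0.5 | −13.3 | −10.7 | −15.9 |
| 1 | −13.3 | −8.2 | −18.4 |

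Simulation with 23 per arm agrees: −10.9 and −15.9 at 0.5 SD, −8.1 and −18.4 at 1 SD, with the unadjusted estimate at about −13.3. With no true effect, the nominal 5% error rate of the adherence-adjusted model becomes about 9% at 0.5 SD and 19–20% at 1 SD. The unadjusted test stays at 5%. The shift in points does not depend on sample size.

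**5. Sensitivity to the assumed form.** A second simulation, with no true drug effect, let adherence depend on arm and on an unmeasured patient factor U: logit adherence = 2 + a × arm − 0.8 × U + noise (SD 0.7), with U shifting PA/A change by b points per SD. The bias was about 0 when a = 0 or b = 0, −3.0 at a = −1, b = 5, and −13.3 at a = −2, b = 10. The last case is strong, since U then explains (10/14.7)² = 46% of the variance. It shows that the 0-to-5 range in step 4 is an illustration and not a bound.

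**The case against.** The strongest reply is that little depends on these models. The primary test is unadjusted and by intention-to-treat, the 46 was sized on it, and the addendum carries the statistical plan forward unchanged for the interim look at 20 participants. Nothing in the plan lets an adherence-adjusted result confirm or overturn the primary one. All of this stands, and it limits the point to a secondary analysis.

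Four stronger readings are tempting, and the documents do not support them:

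- **That the BP rule makes adherence differ by arm.** A patient held back under the rule is following the protocol and might be counted as adherent, non-adherent or dropped out; the recruitment section allows for 25% drop-out. Adherence is undefined, Figure 4 is not shown in the copy reviewed, and the safety section describes sildenafil as usually well tolerated with these pumps. The link is a reasonable inference, not a stated fact.
- **That the drop of under 5 mmHg controls the move to 40 mg.** The first 40 mg dose depends on the acceptable BP range; the drop criterion governs continuing.
- **That adherence displaces a baseline covariate.** The limit of two variables applies at a time, which suggests several small models. Baseline covariates can be used in the others.
- **That the model fails to give an effect of drug if taken.** A common adherence slope would not give one, but the plan never claims that target and does not write the model out.

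The structural point is untouched by any of these: adherence arises after allocation and is treated as if it were a baseline variable.

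**Conclusion.** The point holds and is limited in reach. Any Aim 2 secondary regression that includes adherence, at day 15 or day 8, is not a randomised comparison, and its treatment coefficient may be biased towards or away from zero.

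Bias requires adherence to differ by arm and to be related to PA/A change within arm; if either is absent, it is zero. The documents give no figure for either, so the size is unknown. The illustrated 0 to about 5 points rests on an SD of change of 14.7, an adherence difference of 0 to 1 SD and a correlation of up to 0.35, all three of them assumptions.

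A reader might infer that the trial's intention-to-treat conclusion is compromised. It is not: the primary t test, the 46 patients, the interim criterion of p<0.2 and the models adjusted only for baseline variables are unaffected.

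**What to change.** In Aim 2, Statistical analysis, remove adherence from the list of adjustment variables, so that every covariate is fixed before randomisation. Define adherence, say how doses withheld under the BP rule are counted, and report it descriptively by arm: doses taken, highest dose step reached and reasons for stopping.

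If the effect of drug actually taken is of interest, make it a separate analysis, labelled exploratory, with its target effect and assumptions written down. Using randomised arm as an instrument is one option. It would estimate a complier or per-dose effect under added assumptions, and would be imprecise with about 20 patients. This step is optional.

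The cost is a change of wording plus a short definition. No patients are added, and the sample size and dosing rules do not change.
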